Study Medication:	1. Acyclovir Cream, 5%, Perrigo 2. Zovirax® (Acyclovir) Cream 5%, Valeant Pharmaceuticals 3. Vehicle of Acyclovir Cream, 5%, Perrigo
Study Objectives:	To compare the safety and efficacy profile of Perrigo's Acyclovir Cream, 5% to Zovirax® Cream 5% and to demonstrate the bioequivalence to the reference product as well as superior efficacy of the two active formulations over that of the vehicle in the treatment of herpes labialis (cold sores) in adults and adolescents 12 years of age and older.
Study Design:	Subjects in this multi-center, double-blind, randomized, vehicle-controlled, parallel-group bioequivalence study will be admitted into the study only after written informed consent/assent (as applicable) has been obtained and after all inclusion/exclusion criteria have been met. Male and female subjects, 12 years of age and older, with recurrent herpes simplex labialis will be eligible for enrollment.
Study Population:	██████████ subjects 12 years of age and older, who meet the inclusion/exclusion criteria, will be enrolled.
Dosing:	Subjects will be randomized ██████████ to either the test product, reference product or vehicle treatment group, respectively, and will apply study medication 5 times daily for 4 days. ██████████
Study Visits:	The clinical trial will consist of the following visits: 
• Screening Visit- once the subject meets inclusion/exclusion criteria; they will be randomized and given the study medication. ██████████• Treatment Days: 1 (Visit 2), 2 (Visit 3), 3 (Visit 4), and 4 (Visit 5)• Follow-up Days: 5 (Visit 6), 6 (Visit 7), 7 (Visit 8), 8 (Visit 9), 10 (Visit 10), 12 (Visit 11), 14 (Visit 12), 21 (Visit 13)• ██████████. If healing occurs in-between scheduled study days, the subject should return to the clinic as soon as possible and not wait till the next scheduled visit.

Protocol No: PRG-NY-14-008

Efficacy Assessments:	
The primary efficacy endpoint will be: Time to complete healing of lesions (defined as loss of crust and re-epithelialization with or without erythema, as assessed by the investigator, based on both clinical observation and review of the subject diary), measured in days/hours from the time of first dosing.
 
[REDACTED]

Safety Assessments:	
The incidence of all adverse events reported during the study will be summarized by treatment group. Equivalence of the two active formulations with regard to safety will be evaluated by comparing the nature, severity and frequency of their adverse event profiles. In addition, the frequency and distribution of application site reactions of dry lips, cracked lips, desquamation, dry skin, burning skin, pruritus, flakiness of skin, and stinging of the skin will be summarized for the two active formulations.

Statistical Methods:	
Efficacy
 
The primary efficacy endpoint will be the time to complete healing of lesions (defined as loss of crust and re-epithelialization with or without erythema, as assessed by the investigator, based on both clinical observation and review of the subject diary), measured in days/hours from the time of first dosing.
 
[REDACTED]
 
[REDACTED]
 
[REDACTED]
 
Equivalence of Clinical Endpoint Analysis: The mean time to complete healing of the lesion for the test and reference treatments will be estimated using analysis of Variance (ANOVA) with treatment and center as fixed effects in the model. The 90% confidence interval for the ratio (Test/Reference) of mean time-to-complete healing will be obtained by Fieller's method.
 
A plot for the ratio (Test/Reference) of mean time-to-complete healing and associated 90% CI will be presented.
 
[REDACTED]
 
[REDACTED]. For the time to complete healing of lesion, the Test treatment will be considered to be therapeutically equivalent to the Reference treatment if the calculated 90% confidence interval of the ratio of the means (Test/Reference) falls within the interval of 0.80 to 1.25.

Protocol No: PRG-NY-14-008

	
Analysis of Superiority between active formulation and vehicle: For the time to complete healing of the lesion, subjects who received active treatment will be compared to those who received the Vehicle as treatment in order to determine if superior efficacy has been attained. The time-to-complete healing of both the active products and Vehicle will be analyzed using Analysis of Variance (ANOVA) evaluations with treatment and center as fixed effects in the model.
 
Each active treatment group will be compared to the Vehicle group using a -two-sided test and tested at an alpha level of 0.05. The mean and its 95% confidence interval will be reported. Superiority will be considered demonstrated if the means for both active treatments are statistically different from ($p < 0.05$), and smaller than, that for the Vehicle
 
Safety
 
All adverse events (AEs) will be classified with respect to system organ class (SOC) and preferred term using MedDRA. A treatment-emergent AE is an event that occurs or worsens after the administration of first dose of study medication. The AE profile will be characterized with severity and attribution (unrelated and related) to study medication. Related AEs will be events that are possibly or probably related to treatment in the investigator's judgment.
 
The number and percent of patients who report treatment-emergent AEs will be summarized for each treatment group. Additional summaries by severity and relationship to study medication will be presented for each treatment group. In addition, the number and percent of patients who reported treatment-emergent AEs of interest and serious AEs will be summarized for each treatment group.

Sample Size Considerations:
	

Protocol No: PRG-NY-14-008

ABBREVIATIONS

AE	Adverse Event
ANOVA	Analysis of Variance
CMH	Cochran–Mantel–Haenszel test
CRF	Case Report Form
DCF	Data Clarification Form
FDA	US Food and Drug Administration
GCP	Good Clinical Practice
ICH	International Conference on Harmonization
IGA	Investigator’s Global Assessment
IRB	Institutional Review Board
ITT	Intent to Treat population
mITT	Modified Intent to Treat population
LPN	Licensed Practical Nurse
LVN	Licensed Vocational Nurse
NP	Nurse Practitioner
OTC	Over the Counter
PA	Physician’s Assistant
PI	Principal Investigator
PP	Per Protocol Population
RN	Registered Nurse
Rx	Prescription
SAE	Serious Adverse Event
SAP	Statistical Analysis Plan

Protocol No: PRG-NY-14-008

1. BACKGROUND

[REDACTED]

[REDACTED]

[REDACTED]

[REDACTED]

[REDACTED]

[REDACTED] Zovirax® Cream 5% is indicated for the topical treatment of herpes labialis. Perrigo has developed a generic formulation of Acyclovir Cream, 5%.

2. STUDY OBJECTIVES

The objective of this study is to compare the safety and efficacy profile of Perrigo's Acyclovir Cream, 5% to Valeant's Zovirax® Cream 5% and to demonstrate the bioequivalence of the test product to the reference product as well as superior efficacy of the two active formulations over that of the vehicle in the treatment of herpes labialis in adults and adolescents 12 years of age and older.

Protocol No: PRG-NY-14-008

2.1 Efficacy Endpoints

The primary efficacy endpoint will be the time to complete healing of lesions (defined as loss of crust and re-epithelialization with or without erythema, as assessed by the investigator, based on both clinical observation and review of the subject diary), measured in days/hours from the time of first dosing.

2.2 Safety

Safety of the test and reference products will be compared by evaluating the nature, severity and frequency of their adverse event profiles.

3. STUDY DETAILS

3.1 Study Overview

Subjects in this multi-center, double-blind, randomized, vehicle-controlled, parallel-group bioequivalence study will be assigned [REDACTED] to test product, reference product, or vehicle, respectively. Subjects will apply study medication 5 times daily for 4 days.

3.2 Study Population

[REDACTED] immunocompetent males/females, ≥ 12 years of age with a clinical diagnosis of non-life-threatening recurrent herpes simplex labialis who meet the inclusion-exclusion criteria, will be enrolled in the multicenter study.

3.3 Study Design

Screening Visit:

During Visit 1, once the subject meets inclusion-exclusion criteria, they will be randomized and given the study medication. [REDACTED]

Protocol No: PRG-NY-14-008

[REDACTED]

[REDACTED]

[REDACTED]

Treatment Visits:

Subjects will come in for Day 1 (Visit 2) [REDACTED]. At this visit, they will be questioned regarding onset of the episode. The investigator will identify a target area and mark it in the source document.

Clinic visits will take place on Days 2 (Visit 3), 3 (Visit 4) and 4 (Visit 5).

All subjects must be treated with the study medication for 4 days even if the lesion has healed before treatment ends.

Follow-up visits:

The subjects will return their study medication on Day 5 (Visit 6).

Subsequent follow up visits will take place on:

- Days 6 (Visit 7), 7 (Visit 8), 8 (Visit 9), 10 (Visit 10) and 12 (Visit 11).
- Day 14 (Visit 12) will have a window +/- 1 day (i.e. Day 13-15).
- Day 21 (Visit 13) will have a window of +/- 2 days (i.e. Day 19-23).

[REDACTED]

Note:

If the subject's lesion has healed prior to Day 5 (Visit 6), the subject will continue to apply the study medication as proposed for 4 days, and return for all study Visits up to Day 5 (Visit 6), which will be their End of Study Visit.

Protocol No: PRG-NY-14-008

If the lesion is healed after Day 5 (Visit 6) but before Day 21 (Visit 13), the subject will return for their End of Study visit as directed by protocol upon healing and will not have to continue coming to the clinic for the remaining study visits.

[REDACTED]

[REDACTED]

If a subject arrives to the clinic for an unscheduled visit, the subject will go through the same procedures as a scheduled follow-up day. If the subject has not healed by this unscheduled visit, the subject will return to the clinic for the subsequent previously planned follow-up visits.

The use of the study medication should be discontinued after Day 4; however the investigator will continue to monitor the lesion until Day 21 if not healed by then.

[REDACTED]

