5.9.9 Unscheduled Visit

5.9.10 End of Study Visit/Visit after lesion healing within 24 hours of time to complete lesion healing

Protocol No: PRG-NY-14-008

[REDACTED]							
[REDACTED]							
[REDACTED]						[REDACTED]	[REDACTED]
[REDACTED]							
[REDACTED]							
[REDACTED]							
[REDACTED]	[REDACTED]						
[REDACTED]							
[REDACTED]							
[REDACTED]	[REDACTED]						
[REDACTED]	[REDACTED]	[REDACTED]	[REDACTED]	[REDACTED]	[REDACTED]		

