7.3 Eliciting and Reporting of Adverse Events

The investigator will periodically assess subjects for the occurrence of adverse events.

All adverse events (as defined in Section 7.2), either observed by the Investigator or one of his/her medical collaborators, or reported by the participant spontaneously, or in response to direct questioning, will be reported and documented in the source and the study reporting forms. When reporting an adverse event, the Investigator must assign a severity grade to each event and declare an opinion on the relatedness/ causal relationship of the event to the study medication or procedure. Serious or unexpected adverse events must be reported to Perrigo **within 24 hours** of when the Investigator first learns of the occurrence of the event.

Adverse events will be documented in source and recorded in a timely manner on case report forms. Adverse events that are identified at the last assessment visit (or the early termination visit) must be recorded on the AE case report form (CRF) with the status of the AE noted.

Adverse events will be recorded and reported during treatment and follow-up period. Adverse events should be followed until resolved or 30 days after the final study treatment. In any case, serious adverse events that are not resolved or considered to be chronic within 30 days of the final study treatment must be followed by the investigator until they become resolved or are considered to be chronic (stabilized for at least 30 days). All events that are ongoing at this time will be recorded as ongoing on the CRF.

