6.5.2.1 Definitions

Adverse event (AE)

An adverse event (AE) is any untoward medical occurrence in a subject administered a medicinal product and which does not necessarily have to have a causal relationship with this treatment. An adverse event can therefore be any unfavorable and unintended sign (for example, an abnormal laboratory finding), symptom, or disease temporally associated with the use of a medicinal product, whether or not considered related to this medicinal product.

Serious adverse event (SAE)

Any untoward medical occurrence that meets any of the following criteria:

- Results in death
- Life-threatening event
- Requires in-subject hospitalization or prolongation of existing hospitalization
- Results in persistent or significant disability or incapacity or substantial disruption of the ability to conduct normal life functions
- Results in a congenital abnormality or birth defect
- Any other adverse events that may be considered serious based upon medical judgment

Unexpected adverse event

An unexpected event is any adverse drug experience, the specificity or severity of which is not consistent with the current approved product labeling (package insert) for the study

[REDACTED]

medication, the Investigator's Brochure, or as described in the clinical protocol and consent materials.

Treatment emergent adverse event (TEAE)

Treatment-emergent adverse events (TEAE) are any AEs that occur or worsen (increase in severity and/or frequency) during or after the initial application of the study medication.

For treatment-emergent status regarding events with partial or missing dates, please refer to Section 7.3.

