8.7.4 Other Observations Related to Safety

8.7.4.1 Physical Examination

The physical examination will be performed at Visit 1 (Screening) and Visit 2 (Day 1). A subject listing will be presented which will include:

- Whether physical examination was performed? (Yes/No)
- Examination date
- Were there any abnormal findings? (Yes/No)

8.7.4.2 *Vital Signs*

Vitals signs will be performed at Visit 1 (Screening) and Visit 2 (Day 1). [REDACTED]
[REDACTED]

[REDACTED]

[REDACTED]

8.7.4.3 *Application Site Reaction Assessment*

The severity (none, mild, moderate and severe) of application site reaction will be summarized by frequencies and percentages by visit.

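### After Day 5, adverse event observation lasts only until the lesion heals, so crude TEAE percentages modestly favour the faster-healing arm; a Day 1-5 table would show this at little cost

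*Protocol*

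**What the plan says.** Protocol 3.3 sets three exits from scheduled visits:

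- Healed before Day 5: subjects "return for all study Visits up to Day 5 (Visit 6), which will be their End of Study Visit".
- Healed after Day 5 but before Day 21: anyone in this group "will return for their End of Study visit as directed by protocol upon healing and will not have to continue coming to the clinic", so later scheduled visits are dropped. The heading of Protocol 5.9.10 places this visit within 24 hours of healing.
- Not healed: "the investigator will continue to monitor the lesion until Day 21 if not healed by then", with a Day 19-23 window.

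Dosing lasts four days in every arm, whether or not the lesion has healed.

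On collection, Protocol 7.3 says "Adverse events will be recorded and reported during treatment and follow-up period". Its 30-day provision concerns how long an event already identified is followed. After the last assessment, Protocol 7.3.1 and 7.5.2 rely on the subject to report serious events, and only those judged reasonably associated with study medication are passed on.

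On analysis, SAP 6.5.2.1 defines TEAEs as "any AEs that occur or worsen (increase in severity and/or frequency) during or after the initial application of the study medication", with no closing date. SAP 8.7 and 8.7.2 give subject frequencies and percentages by arm, over everyone dispensed medication, together with event counts. Exposure (SAP 6.5.1, 8.7.1.1) is counted in applications, not in days observed. Application site reactions "will be summarized by frequencies and percentages by visit" (SAP 8.7.4.3).

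On use, Protocol 2.2 states: "Safety of the test and reference products will be compared by evaluating the nature, severity and frequency of their adverse event profiles". The protocol synopsis adds that safety equivalence of the two active products will be judged by comparing these profiles. SAP 8.7 rules out statistical inference on safety.

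**The concern.** From Day 5 onward, the time for which a subject is scheduled to be observed for adverse events is the primary efficacy outcome itself. Two arms with the same tolerability but different healing times will show different crude TEAE percentages, because the slower arm has more days in which a background event can be recorded. The difference arises after randomisation and follows the outcome, so randomisation does not remove it.

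Frequency is one of the three features on which the plan says test and reference will be compared. The trial also aims to show that both actives heal faster than vehicle. If it succeeds, vehicle subjects are observed longer and the actives look somewhat better tolerated by comparison.

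The by-visit table of application site reactions has a related weakness. After Day 5 its rows hold essentially subjects who had not healed before that visit, a group selected by outcome. SAP 6.5.4.3 keeps most site reactions out of the adverse event tables, so this table carries much of the local tolerability evidence.

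**Working it through.** The plan has no figure of its own to reproduce. The sample size sections are redacted, and no AE rate, mean healing time or SD is visible. The size below is therefore an illustration over assumed values.

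**Inputs from the documents.** Observation lasts at least to Day 5, about 4 days after first dose, and at most to Day 21, about 20 days after first dose. The equivalence limit on the healing-time ratio, 1.25, serves as the largest illustrative ratio.

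**Assumptions not in the documents.** Gamma healing times; mean of 5, 7 or 9 days in the faster arm; coefficient of variation (CV) 0.3 or 0.5; slower/faster ratio 1.05, 1.15 or 1.25; a constant daily hazard of a first TEAE of 0.5%, 1%, 2% or 3%, the same in both arms.

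**Formula.** Observed days = healing time limited to 4-20 days. TEAE % = mean of 1 − exp(−hazard × observed days), simulated with 1,000,000 subjects per arm.

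Example with mean 7 days and CV 0.5 (faster vs slower arm):

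| Ratio | Mean days observed | TEAE % at 1%/day | TEAE % at 2%/day |
|---|---|---|---|
| 1.05 | 7.21 vs 7.52 | 6.9 vs 7.2 (+0.29) | 13.2 vs 13.8 (+0.52) |
| 1.15 | 7.21 vs 8.17 | 6.9 vs 7.8 (+0.87) | 13.3 vs 14.8 (+1.59) |
| 1.25 | 7.21 vs 8.81 | 6.9 vs 8.4 (+1.45) | 13.2 vs 15.9 (+2.64) |

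Over the whole grid the difference is +0.1 to +1.0 points at ratio 1.05, +0.3 to +2.9 at 1.15 and +0.5 to +4.8 at 1.25. It always raises the slower arm. In the example, the relative excess is about 4% at ratio 1.05 (0.29/6.9) and about 21% at 1.25 (1.45/6.9).

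**Common window to Day 5.** 1 − exp(−hazard × 4) gives 2.0%, 3.9%, 7.7% and 11.3% at the four hazards, identical in both arms. The equality needs only the same hazard in both arms, not a constant one.

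**Events per subject-day.** Suppose instead that the hazard is 3% per day for the 4 treatment days and 0.5% per day afterwards, in both arms, with 7.2 vs 8.8 days observed.

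- Faster arm: 4 × 3 + 3.2 × 0.5 = 13.6 expected events per 100 subjects.
- Slower arm: 4 × 3 + 4.8 × 0.5 = 14.4, an excess of 14.4/13.6 − 1 = 6%.
- Rates per subject-day: 13.6/7.2 = 1.89 vs 14.4/8.8 = 1.64 per 100. The slower arm now looks 13% safer (1.64/1.89 = 0.87), although tolerability is identical.

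Dividing by days observed therefore reverses the bias when events cluster during treatment.

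**The case against.** The case for leaving the plan alone has real weight.

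- SAP 8.7 makes safety descriptive. No test, margin or decision rule depends on a TEAE percentage. This stands.
- All subjects are scheduled through Day 5, so the treatment period is covered equally. Only events starting after dosing ends are affected, and these are mostly background. The treatment-related TEAE tables, with causality judged blind, are less exposed. This stands.
- The stated safety objective is test versus reference. Vehicle enters the objectives only for efficacy. If test and reference heal alike, the distortion between them is small. This stands.
- Late-onset events matter, and a Day 5 cut-off removes them from a comparison. Protocol section 7 mentions contact dermatitis and eczema, some of which could start after Day 5. That is a reason to read the Day 5 table with the whole-study tables, not in their place.
- The site reaction rows for Visits 2-6 already exist. Only the emphasis and a footnote are missing.
- Protocol 3.3, the visit procedures and the assessment schedules are partly redacted. A later contact for all subjects cannot be excluded; none is visible.

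These points limit the size and importance of the problem but do not remove it. The synopsis says AE frequency will be compared to judge safety equivalence, so the tables will be read as a comparison even without a test.

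**Conclusion.** The mechanism holds on the visible text. Scheduled AE observation runs to Day 5 for everyone and then to healing or Day 21, and nothing visible in the TEAE definition, denominators or exposure summaries allows for the difference. The direction is certain if arms heal at different speeds and background events continue after Day 5. The size is not: the range of about +0.1 to +1.0 points at a healing ratio of 1.05 and +0.5 to +4.8 at 1.25 rests on assumed AE rates, assumed healing times and a constant hazard.

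A reader might infer that the safety comparison of test and reference is inflated by about a fifth. The documents do not support that. It needs a true ratio at the 1.25 equivalence limit, where a product should pass at most about 5% of the time, and it needs events to continue after treatment at the same rate as during it. At 1.05 the relative excess is about 4% in the example above. Nor do the documents support reading this as damage to a safety test, since none is planned.

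This is a minor point with a cheap remedy. Confidence is moderate because of the redactions.

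**What to change.** In SAP 8.7.2, add a between-arm table of TEAEs, overall and treatment-related, with onset from first application through Day 5 (Visit 6), the interval scheduled for every subject. State that it will be used together with the whole-study tables, which are kept, when AE frequency is compared. Beside the whole-study tables, tabulate observation time by arm. Do not rely on events per subject-day to correct for unequal follow-up, for the reason shown in the working.

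In SAP 8.7.4.3, base the arm comparison of application site reactions on Visits 2-6, and footnote later rows as limited essentially to subjects not healed before that visit.

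If redacted text provides a later safety contact for all subjects, the SAP should say so and define the TEAE period by it.

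The cost is SAP wording and a few extra tables from dates already collected, with no added visits or subjects. The downside is that late-onset events appear only in the whole-study tables, which is why those must be kept and read alongside.

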4. SELECTION AND WITHDRAWAL OF STUDY SUBJECTS

4.1 Inclusion Criteria

Subjects **must** meet all of the following criteria:

1. Immunocompetent (defined as not having underlying disease and/or the administration of immunosuppressant medication) male or nonpregnant females, 12 years of age and older, with non-life-threatening recurrent herpes simplex labialis.
2. Subjects must have [REDACTED] recurrences of herpes simplex labialis per year for the past [REDACTED] years.
 - a. [REDACTED] recurrences preceded by recognizable prodromal symptoms [REDACTED]
 - b. [REDACTED] prodromes followed by classical lesions.
3. Subject must sign an Institutional Review Board (IRB) approved written informed consent for this study prior to study related procedures being performed. Subjects under the legal age of consent must sign an IRB approved written informed consent/assent in addition to a parent or legally authorized representative.

Protocol No: PRG-NY-14-008

4. Subjects must be willing and able to understand and comply with the requirements of the study, apply the study medication as instructed, refrain from use of all other topical medication or topical antibiotics near the area of the cold sore during the treatment and follow up periods of the study, return for the required study visits and comply with therapy prohibitions.

5. Subjects must be in general good health and free from any clinically significant disease that might interfere with the study evaluations in the opinion of the investigator.

6.

